5.1.3. EXPOSURE TIME

Time at risk will start on index date and continue until first treatment discontinuation (see definition in Section 5.1.6). Continuous exposure will be defined as successive exposure periods for the study drugs separated by gaps of 30 days at most. Duration of exposure

Proprietary confidential information © 2024 Boehringer Ingelheim International GmbH or one or more of its affiliated companies

episodes for individual prescriptions of study drugs will be derived based on package size, unit strength and daily dose.

To account for an empirical induction/promotion period of cancer, a latency period of 6 months (180 days) after the index date is applied. Patients with less than 6 months (180 days) of follow-up time will be excluded. In addition, patients with any diagnosis of any cancer within the latency period will be excluded. In a sensitivity analysis, the latency period will be extended to 12 months (365 days).

* Other drugs: a prescription of another drug (empagliflozin, a DPP-4 inhibitor, or a SGLT-2 inhibitor) other than index drug

Figure 1 Definition of continuous exposure period of index drug

For the primary AT analyses, the time at risk will begin after the latency period and end at urinary tract (bladder, renal or other) cancer or at any of the censoring events (listed in Table 4), whichever occurs first. In addition, treatment discontinuation of the index drug (defined in Section 5.1.6) is an additional censoring variable.

For the sensitivity ITT analyses, the time at risk will begin after the latency period and end at urinary tract (bladder, renal or other) cancer or any of the censoring events excluding treatment discontinuation of the index drug.

Patients with censored time at risk will not be able to re-enter the study cohort at a later time point. The time at risk will not be censored if oral or injectable glucose-lowering drugs other than the index drugs and SGLT-2 inhibitors are prescribed in addition to empagliflozin or a DPP-4 inhibitor after the index date.

Proprietary confidential information © 2024 Boehringer Ingelheim International GmbH or one or more of its affiliated companies

Table 4 Censoring events.

Censoring event	Definition	Data source
All-cause mortality	Censoring of follow-up time occurs at the date of death regardless of the cause. Applied in all analyses.	UK: CPRD-GOLD and Aurum Sweden: Cause of death register Finland: Cause of death register

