Emigration from the study country	Censoring of follow-up time occurs at the date of emigration from the study country. Applied in all analyses.	UK: CPRD-GOLD and Aurum Sweden: Total population register ¹ Finland: Population register centre
Patient transfer	Censoring of follow-up time occurs at the date of patient transfer. Applied in all analyses.	UK: CPRD-GOLD and Aurum Sweden: NA Finland: NA
Incidence of any cancer during follow-up	A registered diagnosis of any cancer (excluding non-melanoma skin cancer) during follow-up. (ICD-10, ICD-7, ICD-O-3 and READ diagnosis codes in Annex I) Applied in all analyses.	UK: CPRD-GOLD and Aurum Sweden: Swedish cancer registry (SCR) Finland: FCR
Diabetes diagnosis other than type 2	A diagnosis of type 1 diabetes or other non-type 2 diabetes during follow-up identified using the same algorithm as used for the exclusion criteria (Section 4.2.4) Relevant ICD-10 codes and READ diagnosis codes are provided in Annex I. Applied in all analyses.	UK: CPRD and Aurum Sweden: NDR, NPR Finland: reimbursement registry
End of study period	Censoring of follow-up time occurs at end of study date i.e. 31 December 2020 (2021 for UK-CPRD). Applied in all analyses.	NA

Proprietary confidential information © 2024 Boehringer Ingelheim International GmbH or one or more of its affiliated companies

Treatment discontinuation (AT exposure- main analysis)	Censoring of follow-up time occurs 90 days after 
 - last day of medication (i.e. stop date) - new prescription of the other study drug or of a SGLT-2 inhibitor Applied only in analyses using the AT exposure definition.	UK: CPRD-GOLD and Aurum Sweden: SPDR Finland: FPR
Treatment discontinuation (AT exposure- sensitivity analysis)	Censoring of follow-up time occurs 180 days after 
 - last day of medication (i.e. stop date) - new prescription of the other study drug or of a SGLT-2 inhibitor Applied only in the sensitivity analysis using the AT exposure definition.	UK: CPRD-GOLD and Aurum Sweden: SPDR Finland: FPR

¹ The National patient register will be used if data on immigration/emigration are unavailable from the Total population register.

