5.1.6. Definition of continuous treatment and discontinuation

Continuous treatment

Continuous treatment is defined as having consecutive treatment episodes separated by a grace period of 30 days (Figure 1). In a sensitivity analysis, the grace period is extended to 90 days.

In case of overlaps between treatment episodes (i.e., a new prescription/dispensation during an ongoing exposure period), the overlapping days are added to the end of the following treatment episode, resulting in a longer treatment episode to take into account possible stockpiling.

Treatment discontinuation

Treatment discontinuation (see Table 4) is defined either by

- The start of a new prescription of any new drug from the following drug groups: empagliflozin, DPP-4 inhibitors, or SGLT-2 inhibitors), or of a fixed-dose combination of a SGLT-2 inhibitor with a DPP-4 inhibitor (identified from the ATC class A10BD)
- The end date of the first continuous exposure period of the index drug (stop date) plus a 3-month (90 days) period following it.

The discontinuation date is defined as the stop date/start date of a new drug plus 90 days.

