5.1.7. Primary Exposure definition

The primary definition of exposure, i.e. as-treated exposure (AT), is defined as a continuous exposure to empagliflozin or to a DPP-4 inhibitor, starting from index date. Continuous exposure and treatment discontinuation are defined in Section 5.1.6.

In the Swedish dataset, drug exposure will be identified from SPDR. In Finland, the FPR will be used. In the UK datasets, drug exposure will be identified from CPRD data. The study drugs will be identified using ATC codes (med codes for CPRD) listed in Annex II.

Proprietary confidential information © 2024 Boehringer Ingelheim International GmbH or one or more of its affiliated companies

Table 5 As-treated exposure definition

Exposure	Definition	Details	Data source
Exposure to index drugs (as treated)	Exposure status for empagliflozin (alone or in combination with metformin) or DPP-4 inhibitor (including combinations) based on purchased amounts and daily defined dose. ATC codes for empagliflozin and DPP-4 inhibitors in Annex II.	Time-fixed Categorical: Empagliflozin DPP-4 inhibitor	UK: CPRD Sweden: SPDR Finland: FPR
Evaluated at index date			

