5.1.8. SECONDARY EXPOSURE DEFINITIONS

Exposure definitions based on dosage or duration

Table 6 Exposure definitions based on dosage or duration

Exposure	Definition	Details	Data source
Cumulative dose of empagliflozin use in grams	Time-updating cumulative sum of empagliflozin dose consumption based on the daily prescribed dose and purchased amounts since the start of follow-up. ATC codes for empagliflozin in Annex II.	Time-dependent Categorical ¹ : Never 0 - <cumulative dose Q1 ≥ Q1 to < Q2 ≥ Q2 to < Q3 ≥ Q3	UK: CPRD Sweden: SPDR Finland: FPR
Daily dose of empagliflozin	The dosage of empagliflozin prescribed per daily use (10mg vs. 25mg). ATC codes for empagliflozin in Annex II.	Time-dependent Categorical: Never 10 mg 25 mg	UK: CPRD Sweden: SPDR Finland: FPR
Updating from index date onwards.*			

Proprietary confidential information © 2024 Boehringer Ingelheim International GmbH or one or more of its affiliated companies

Cumulative exposure duration to empagliflozin in months	Time-updating cumulative sum of duration since the first use of empagliflozin (alone or in combination with metformin), in months. ATC codes for empagliflozin in Annex II.	Time-dependent Categorical ² : Never 0 - < cumulative duration Q1 Updating from index date onwards.* ≥ Q1 to < Q2 ≥ Q2 to < Q3 ≥ Q3	UK: CPRD Sweden: SPDR Finland: FPR
---	--	--	--

*The last observed value will be carried forward for 3 months (90 days) to account for the 90-day delay between end of treatment and treatment discontinuation as defined in Section 5.1.6.

¹ The categories are defined based on the quartiles of overall cumulative dose (grams) of the study population

² The categories are defined based on the quartiles of overall cumulative exposure duration (months) of the study population

Intention-to-treat exposure definition

The intention to treat exposure definition assumes that individuals do not discontinue the treatment of an index drug.

Table 7 Intention-to-treat exposure definition

Exposure	Definition	Details	Data source
Exposure to index drugs (Intention to treat)	Purchase of empagliflozin (alone or in combination with metformin) or any DPP-4 inhibitors (including combinations). ATC codes for empagliflozin and DPP-4 inhibitors in Annex II.	Time-fixed Categorical: Empagliflozin	UK: CPRD Sweden: SPDR Finland: FPR

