Meta-analysis of adjusted HR estimates	Using adjusted HR estimates with 95% CIs from all study countries (9 figures, 3 outcomes x 3 secondary exposure)	3 secondary exposure definitions listed above	Main outcomes- Table 8	Figure 8

Sensitivity analysis: NCC study design

Balance assessment for baseline characteristics between matched cases and controls.	Country specific analysis (3 tables, one for each country)	N/A	N/A	Table 33
Odds ratio using conditional logistic regression	Nested case-control study design. (3 tables, 1 outcome (all cancer cases) x 3 countries)	As treated exposure definition	All cancer cases defined in Table 8	Table 34
Meta-analysis for odds ratio estimates	Using odds ratio estimates with 95% CIs from all study countries (1 figure, 1 outcome (all cancer cases))	As treated exposure definition	All cancer cases defined Table 8	Figure 8

Analysis	Details	Exposure definition	Outcomes	Template
Sensitivity analysis: Adjusting for time-dependent confounding				
Hazard ratio estimates using marginal structural model	Using matched cohorts MSM using IPTW. (3 tables, 1 outcome x 3 countries)	As treated exposure definition	Urinary tract cancer as defined in Table 8	Table 35
Meta-analysis of adjusted HR estimates using MSM	Using adjusted HR estimates with 95% CIs from all study countries (1 figure, 1 outcome)	As treated exposure definition	Urinary tract cancer as defined in Table 8	Figure 8
Sensitivity analysis: Exposures				
Hazard ratio estimates using adjusted model	Using matched cohorts (3 tables, 1 outcome x 3 countries)	Intention to treat exposure definition	Urinary tract cancer as defined in Table 8	Table 25
Meta-analysis of adjusted HR estimates	Using adjusted HR estimates with 95% CIs from all study countries (1 figure, 1 outcome)	Intention to treat exposure definition	Urinary tract cancer as defined in Table 8	Figure 8
Sensitivity analysis: Grace period				
Hazard ratio estimates using adjusted model	Using matched cohorts Allowed gaps between exposure episodes extended to 90 days (3 tables, 1 outcome x 3 countries)	Intention to treat exposure definition	Urinary tract cancer as defined in Table 8	Table 25
Meta-analysis of adjusted HR estimates	Using adjusted HR estimates with 95% CIs from all study countries (1 figure, 1 outcome)	Intention to treat exposure definition	Urinary tract cancer as defined in Table 8	Figure 8

Analysis	Details	Exposure definition	Outcomes	Template
Sensitivity analysis:				
Outcomes				

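### SAP Table 16 lists the 90-day grace-period sensitivity analysis under intention to treat, where the gap length changes nothing

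*SAP*

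**What the plan says.** Section 5.1.6 of the SAP defines continuous treatment as successive episodes separated by a grace period of 30 days, and adds: "In a sensitivity analysis, the grace period is extended to 90 days". Section 5.1.7, which defines AT exposure, relies on that section: "Continuous exposure and treatment discontinuation are defined in Section 5.1.6". Item 14 of the SAP's change table (Section 3) gives the purpose of the added analysis as assessing the effect of the longer grace period, and points to Section 6.8.3.

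Table 16 in Section 6.10 has two rows under its grace-period heading: country-level hazard ratios and their meta-analysis. The first is described as "Allowed gaps between exposure episodes extended to 90 days". The exposure column of both rows reads "Intention to treat exposure definition".

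On intention to treat, Section 5.1.8 states: "The intention to treat exposure definition assumes that individuals do not discontinue the treatment of an index drug". Section 5.1.3 ends ITT time at risk at urinary tract cancer or "any of the censoring events excluding treatment discontinuation of the index drug". Table 4, in the same section, says of censoring at treatment discontinuation: "Applied only in analyses using the AT exposure definition".

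**The concern.** The grace period exists to decide when a patient has stopped the index drug. An ITT analysis ignores stopping, so lengthening the grace period within it should leave the result where it was. The listed rows therefore appear unable to serve the purpose given in the change table.

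What is at stake is the only visible check on the 30-day rule. Under AT, that rule ends follow-up 90 days after the stop date and the patient cannot re-enter (Section 5.1.3). Days' supply for the study drugs is derived from pill strength and recommended dosage (Section 5.1.4), and Protocol 8.3.1 gives a typical prescription length of three months in Sweden and Finland. Protocol 8.9 acknowledges that exposure may be misclassified and promises sensitivity analyses of the effect of exposure definitions on the main results, which are AT results. A grace-period output that repeats ITT would look like reassurance on this point and give none.

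**Working it through.** The plan states no figure to reproduce. The check is to trace where the gap enters, and then apply the follow-up rules to an example.

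**Where the gap enters**

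1. Gap length determines the first continuous exposure period (5.1.6).
2. The end of that period is the stop date (5.1.6).
3. Stop date + 90 days is the censoring date for discontinuation (5.1.6, Table 4).
4. That censoring is used only in AT analyses (Table 4); ITT time at risk excludes it (5.1.3).

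Other possible routes:

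- *Exposure variable.* AT and ITT exposure are both time-fixed at index (Tables 5 and 7). They differ only in censoring at discontinuation.
- *Model covariates.* The time-dependent terms in the adjusted model (6.7.2) are HbA1c, stones, UTI and ever-exposed indicators for other glucose-lowering drugs. None depends on the study-drug gap.
- *Entry to the cohort.* The latency exclusion is worded as follow-up: "Patients with less than 6 months (180 days) of follow-up time will be excluded". ITT follow-up does not end at discontinuation, so on this wording the gap does not alter who is included.

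**The rows side by side (Table 16)**

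| | ITT rows | Grace-period rows |
|---|---|---|
| Cohort | matched | matched |
| Model | adjusted | adjusted |
| Outcome | urinary tract cancer | urinary tract cancer |
| Exposure | ITT | ITT |
| Output | 3 tables, 1 figure | 3 tables, 1 figure |
| Templates | Table 25, Figure 8 | Table 25, Figure 8 |

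The only difference is the gap, which has no route into the result. By contrast, the sensitivity analysis that moves the post-stop window to 6 months is listed under AT.

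**One patient**

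Assumed history, not from the documents: 90-day supplies at days 0, 90, 180 and 270; the next fill 60 days late at day 420; then on time at days 510, 600 and 690; no stockpile; no other censoring event before day 870. Time at risk starts at day 180.

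- AT, 30-day rule: supply ends at 270 + 90 = day 360. The gap is 420 − 360 = 60 > 30, so the stop date is day 360. Censoring is at 360 + 90 = day 450. Time at risk = 450 − 180 = **270 days**.
- AT, 90-day rule: the 60-day gap is bridged. The stop date is 690 + 90 = day 780. Censoring is at 780 + 90 = day 870. Time at risk = 870 − 180 = **690 days**.
- ITT: follow-up ends at the same non-discontinuation event under either rule. Difference = **0 days**.

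**A simulated cohort**

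Assumptions, again not from the documents: 20,000 patients, 90-day supplies, exponential refill gaps with mean 25 days, a 5% chance of stopping at each refill, 165 cancers per 100,000 person-years, exponential death times with mean about 40 years, and administrative censoring uniform between 200 and 2,300 days.

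| Rule | Gap | Patients | Person-years | Events |
|---|---|---|---|---|
| ITT | 30 days | 19,725 | 55,191.94 | 106 |
| ITT | 90 days | 19,725 | 55,191.94 | 106 |
| AT | 30 days | 13,281 | 9,681.75 | 15 |
| AT | 90 days | 18,281 | 34,482.50 | 61 |

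The size of the AT change follows from the assumed refill pattern. What carries over is that ITT does not move and AT does.

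**The case against.** The case for leaving this alone has four parts.

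- *Section 6.8.3 is not in the supplied text.* It is the section the change table cites for this analysis, and it may name AT. If it does, the analysis is properly specified there and Table 16 carries a wrong label. That limits the consequence, but Table 16 would then conflict with 6.8.3 as well as 5.1.6 and would still need correcting.
- *The 180-day exclusion could be read as an exposure requirement.* Protocol 8.9 says the 6-month lag is applied in both AT and ITT analyses to remove patients with only short exposure, and SAP 5.1.3 sits under a heading about exposure time. If the ITT cohort were first restricted by AT follow-up, the gap could change who enters and the result would not be an exact repeat. The SAP does not say this: the exclusion is stated as follow-up time, Protocol 8.9 itself applies the lag to follow-up time, and ITT follow-up has its own rule. The zero-difference statement should nevertheless be understood as resting on that reading. Even on the other reading, ITT would be a poor vehicle for testing a discontinuation rule.
- *It looks clerical, and quality control may catch it.* Table 16 has other slips; for example, the base-model row points to Table 23 where 6.7.2 names Table 24. Section 10 requires a second statistician to check the programs. But that check is against the SEAP and its shells, so a faithful run of Table 16 could pass.
- *The reach is small.* One sensitivity analysis on one outcome is affected, and the 6-month post-stop analysis and ITT itself also probe discontinuation. This is fair. Those two analyses, however, respectively extend time after the same stop date and drop discontinuation altogether; neither isolates the gap rule.

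**Conclusion.** Table 16 is wrong as written. As listed, the grace-period analysis cannot show the effect of a longer grace period: relative to the ITT rows above it, the change in follow-up is 0 days for every patient, given that the 180-day minimum is follow-up time as the SAP states. The intended comparison under AT can move follow-up substantially for a patient with a refill gap between 30 and 90 days (270 against 690 days in the assumed history), though nothing here estimates the effect on the hazard ratio. No primary or secondary estimate is affected. The loss is the one visible test of the 30-day rule, together with an output whose label would misdescribe it. That no other analysis varies the gap is established only for the supplied text.

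**What to change.** In both grace-period rows of Table 16, change the exposure definition from ITT to as treated, and confirm that Section 6.8.3 says the same. The cost is two table cells and one cross-check, with no additional analyses.

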7. DATA MANAGEMENT

█████ will collect electronic patient records and comply with procedures that include checking electronic files, maintaining security and data confidentiality, following analyses plans, and performing quality checks for all programs.

█████ will maintain any patient-identifying information securely on site according to up-to-date standard operating procedures. █████ will also maintain appropriate data storage, and archiving procedures will be followed with periodic backup of files.

8. STATISTICAL SOFTWARE

R language (<http://www.r-project.org>) will be used in statistical analysis for creating tabulations and graphics as well as in all statistical modelling. R language is described in more details in report "R: Regulatory Compliance and Validation Issues: A Guidance Document for the Use of R in Regulated Clinical Trial Environments" (www.r-project.org/doc/R-FDA.pdf, read 21 December 2016)[12].

9. MISSING DATA

A high frequency of missing values is not expected for most variables, with the possible exception of lifestyle and biological measurement variables. For the medical history conditions / comorbidities to be collected for inclusion in the propensity score, the absence of a code for a condition will be interpreted as an absence of the event.

If a variable is missing for only some of the patients, a missing data category will be added and utilized in the analysis. If a variable is missing for more than 50% of patients, removal of the variable from the relevant model or analysis (propensity score, multivariable Cox's regression, NCC matching) will be considered.

10. QUALITY CONTROL

The data analysis will be conducted as specified in the SEAP. The principal investigator, the co-investigators and the sponsors of the study must approve all revisions to the SEAP. All major changes to the SEAP shall be properly documented as SEAP amendments and when necessary such SEAP amendments will be implemented in the study protocol and delivered to relevant ethics committees and register holders.

█████ will be the registered holder for the retrieved Swedish, Finnish and UK data, also with the responsibility for destroying the data after the study, when legally possible. A quality control will be performed on the retrieved register data, including the inclusion of compulsory variables, such as SID and main diagnosis, in the delivered register data. If data are missing or incorrect, the dataset is sent back to the register holder for correction.

All processes from data management leading to dissemination of study results will undergo quality control checks for programs, result tables and written text, according to █████'s Standard Operating Procedures and project-specific instructions RWI_WI_EPI0010 "Non-Interventional Study and Low Intervention Clinical Trial Report Development", RW_PI_OP-401.01_003_01 "Programming and statistical analysis", and RW_PI_OP-406.01_003_01 "Programming validation". A detailed audit trail of all documents (programs, result tables, reports) along with quality control processes will be maintained.

All programs for data management and data analyses written by study statistician(s) will be self-documenting with comments about the data handling process, the population selection and the analysis performed by the program. The documentation will be sufficient for another statistician to be able to repeat the program. A statistician other than the one who writes the program will carry out quality control checks of these programs. The programming QC will be performed for all programs related to the database, its individual datasets from different registers and statistical analyses. The QC will be documented with the following information:

- Name of the program
- Purpose of the program
- Name of the programmer
- Validation status and date of validation
- Updates and dates of updates
- Name of the QC statistician
- QC findings or comments
- Date of QC

The statistician responsible for the QC of a program will ensure that:

- The correct dataset and population has been used
- The analysis is carried out according to the SEAP
- The analysis results are consistent
- The output is in line with the table shells in the SEAP
- The analysis can be interpreted in both statistical and clinical terms.

All QC findings by the QC statistician will be documented, and corrections are made to the programs accordingly. All changes are documented as updates to the original program.

The raw dataset and statistical programs used for generating the data included in the final study report will be kept in electronic format and be available for auditing and inspection.

As the register holder of the study register [REDACTED] is in charge of archiving and deleting the data. Secure archives will be maintained for the orderly storage and retrieval of all study related material. An index shall be prepared to identify the archived contents and their location. Access to the archives will be controlled and limited to authorised personnel only. Access to the study data cannot be given to any third parties, neither the study data can be used to other purposes than prescribed in the study protocol. All requests to use the study data for other purposes than mentioned in the study protocol must be subjected to appropriate data permit processes.

